9.2.1 Eligibility for study

Ages:	18-60 years
Genders:	Both male and female
Health status:	Good state of health both somatically & psychologically

9.2.2 Inclusion Criteria:

- Healthy individuals with no apparent disease and normal routine laboratory parameters during screening
- Healthy individuals identified as fit for proving by experts
- Intelligent enough to record carefully the facts, subjective and objective symptoms generated by the IPS during proving.
- Able to be informed of the nature of the study and willing to give written informed consent

9.2.3 Exclusion Criteria:

- Any disease or condition which might compromise the hematopoietic, renal, endocrine, pulmonary, central nervous system, cardiovascular, immunological, dermatological, gastro-intestinal or any other body system
- Persons with colour blindness.
- Persons who have undergone surgery in last two months.

- Planned medical / dental treatment during the proving period including herbal or dietary supplements, procedures, or medications that are likely to interfere with, or substantially alter, responsiveness to the proving substance.
- Volunteers on regular medication (allopathic, ayurvedic, homoeopathic, naturopathic, unani, etc.) for any acute or chronic disease.
- Participant must not be on any homoeopathic remedy in the preceding one month and have had no significant change in health status in last one month.
- Emotionally disturbed, hysterical or anxious persons.
- Persons having known history of allergies, food hypersensitivity, etc.
- Women during pregnancy, puerperium and while breast-feeding and women who have undergone hysterectomy.
- Smokers who smoke more than 10 cigarettes per day
- Recent history of alcoholism / drug addictions or unlikely to refrain from excessive alcohol consumption / drug intake during the study period
- Participation in another clinical or proving trial during the last 6 months

9.3 Sample size:

Each drug will be proved on a minimum of 30 participants, including 30% control. Adding 20% dropout, minimum volunteers needed to enroll in proving becomes 40. Each centre must enroll minimum 15 to a maximum of 25 volunteers in proving. Efforts are to be taken to include atleast 20% volunteers from non-homoeopathic background.

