9.4.8 Blinding

The study will be a double blind study, where the site investigators and the participants at the study site will be kept blind about nature of drug substance and the allocation of participants in the verum and placebo groups. The study medication will be sent in coded forms along with a randomization chart. The nature of the proving substance will be known to the PI and the Co-I/coordinator, but the site investigators and the participants will be blind to the nature of the IPS. The coded study medication will be labeled with the UIC and sent to the proving site.

9. 4.9 Interventions

10.3.1 Arms	Assigned Interventions
Group I : IPS	The verum group will be advised to take the study medication as per schedule. This group will comprise of about 70% of the enrolled participants. The IPS will be given in multiple batches, out of which 1 batch will be placebo and other batches will be IP.
Group II: Placebo	The control group will be given placebo indistinguishable from the study medication. This group will comprise of about 30% of the enrolled participants. Multiple batches will be given, all of which will comprise of placebo.

Both the drug and the placebo will be same in appearance, odor and taste.

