9.4.13 Route & Method of administration of IP/placebo

The IPS/placebo will be sent as study medication to the proving site. The study medication will be prepared in batches for each individual prover. A minimum of 3 batches is proposed for one proving. Each batch will comprise of the drug/placebo in globules of size 30. Study medication used in this drug proving will be administered orally as globules, the content of which is allowed to be absorbed orally.

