13.4 Compilation of Proving symptoms

The sign(s) &/or symptom(s) generated in each prover after the end of each drug batch will be noted along with their prover code, name of the proving center, number of doses after which each of the signs or symptoms appeared and the duration for which they persisted. The sign(s) &/or symptom(s) generated in the drug group will be segregated from those of the control group. In the intervention group sign(s) &/or symptom(s) generated during intake of placebo batch will be segregated from those appearing during IP intake. The sign(s) &/or symptom(s) which are identical (exactly the same in terms of location, sensation, modalities, concomitants) in both drug and placebo will not be included as proving symptoms.

These proving symptoms will be identified. These proving symptoms will be compiled and arranged as per the schema of the Kent's Repertory i.e. Mind, Vertigo, Head, Eye, Ear,etc.

To each sign and symptom generated, the following information will be linked:

- Prover code: Number
- Prover gender: M/F
- Proving Center: XX
- Day of symptom appearance (Day 1 being the day of administration of the study medication batch)
- Time of day of symptom occurrence (HH:MM) *(if information available)*
- Characterizing feature(s)
- Duration for which the symptom persisted in terms of hours/days
- Potency of the IPS in the study medication batch

This information would then be the basis where the following types of symptoms are distinguished:

- Characteristic symptoms (if reported)
- Ongoing symptoms that have unexpectedly and markedly improved
- Proving symptoms with one or more characterizing features

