14. DATA ANALYSIS

14.1 Qualitative analysis:

14.1.1 Symptom selection criteria:

Drug proving data is in the form of symptoms, where there is no measure of efficacy, but description of individual proving symptoms where qualitative research evaluation will be applied. The evaluation will be done by compilation of the proving symptoms in different categories, representing a certain probability to be associated with the remedy and therefore are the most important ones for further clinical verification.

Example: a symptom will belong to the remedy with great probability if at least one of the following criteria is met^[5].

- Occurrence of the symptom in two or more volunteers
- Objective, measurable signs corroborating with the symptoms
- Distinct intensity of the symptom
- Occurrence of the symptom several times shortly after administration of the drug
- Recurrence of the symptom several times over the course of a number of days
- Recurrence of the symptom using different potencies
- Striking, singular, uncommon symptoms
- Striking, seldom or paradox modalities and/or concomitants of the symptom

However, all symptoms including those appearing in lesser number of provers, less distinct or common symptoms will all be included in the proving data. Symptoms, which are not thought to belong to the drug picture, would also be stated, but under separate headings, marked in a specific manner so they are not lost for clinical verification. Such symptoms may be compared with the clinical verification symptoms at a later stage if required.

14.1.2 Characterizing features of proving symptoms:

All provers are to be included in the analyses. The symptoms obtained under verum or placebo must be listed separately. The proving symptoms are identified and their characterizing feature^[9] will be detailed:

- A.** New symptoms with marked severity, duration or frequency
- B.** Ongoing or recurring symptoms present during the proving that have been unexpectedly and markedly improved
- C.** Ongoing or recurring symptoms that have been unexpectedly and markedly worsened
- D.** Symptoms that recur from the past but have not occurred in the 12 months preceding the proving
- E.** Symptoms that display alteration with another symptom in a single volunteer in such a way that the alteration is strongly individualizing
- F.** Symptoms associated with modalities or concomitant symptoms occurring in other parts of the same prover

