- G.** Symptoms that involve multiple body parts or organs in a similar manner or multiple symptoms within the same subject with a similar associated modality, forming an easily recognizable pattern of reaction
- H.** Similar symptoms occurring in multiple provers. Such symptoms may be related by similar sensation, modality, or body system and can be recognized through a qualitative analysis similar to red – line symptom reporting in homoeopathic literature.
- I.** Any objective finding/including abnormal laboratory values associated with subjective symptoms.

14.1.3 Grading of the Drug Proving Symptoms as per their value:

Symptoms will be graded as follows:

Grade I symptoms:

- Symptoms appearing in more than 2 provers, at two different study sites (Symptom in 1 or more prover at one site and similar symptom in 1 or more provers at the second site. i.e. if two provers separated by distance and time with no contact with each other what so ever give the same symptom).
- Peculiar, rare, queer, strange, characteristic symptoms
- Symptoms reappearing from prior provings.

Grade II symptoms

All proving symptoms other than those in grade I

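### Drug symptoms are removed only on an exact match to placebo, yet recurrence across provers is accepted on mere similarity, and the looser grouping is never applied to placebo

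*Protocol*

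**What the plan says.** - **Exclusion (protocol 13.4).** Symptoms that are "identical (exactly the same in terms of location, sensation, modalities, concomitants) in both drug and placebo will not be included as proving symptoms". This is the only stated rule by which placebo data remove a symptom.
- **Feature H (14.1.2).** This characterizing feature covers similar symptoms in several provers: "Such symptoms may be related by similar sensation, modality, or body system". Any one of the three links is enough.
- **Grade I (14.1.3).** The recurrence bullet asks for more than two provers at two sites. Its parenthesis explains this as "Symptom in 1 or more prover at one site and similar symptom in 1 or more provers at the second site", then restates it as two unconnected provers giving the same symptom. The bullet therefore carries both standards.
- **Other recurrence criteria (14.1.1).** A symptom probably belongs to the remedy if any one listed criterion is met. One of them is "Occurrence of the symptom in two or more volunteers", and another is recurrence across potencies. The wording here is *the symptom*, not a similar one.
- **Placebo.** Section 14.1.2 has verum and placebo symptoms listed separately. No section groups placebo symptoms by similarity or compares recurrence under drug with recurrence under placebo.

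**The concern.** The match that counts against the drug is strict on four attributes at once. The match that counts for it can rest on one attribute. Take a verum headache worse from noise. It is kept although placebo provers had headaches worse from light, because the modality differs. On the broadest reading of feature H, it then recurs in any other verum prover with a head symptom.

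Background complaints pass a four-attribute identity test easily and find partners within a body system easily. Some recurrence will therefore appear with an inert drug, and the placebo control as written cannot remove it. Grade I is the higher of the two grades, so its ranking of symptoms could partly reflect background.

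**Working it through.** **Inputs from the protocol**
- Provers (9.3): "Each drug will be proved on a minimum of 30 participants, including 30% control", so 21 verum and 9 placebo.
- Enrolment (9.3): "Adding 20% dropout, minimum volunteers needed to enroll in proving becomes 40". Check: 30/(1 − 0.20) = 37.5, or 38, and 40 is this rounded up. Enrolment of 40 gives 28 verum and 12 placebo.
- Batches (9.4.13): "A minimum of 3 batches is proposed for one proving".
- Verum group (9.4.9): "out of which 1 batch will be placebo and other batches will be IP". With three batches, each verum prover has two drug batches and one placebo batch.
- At 21/9 there are 21 × 2 = 42 drug batches and 21 + 9 × 3 = 48 placebo batches. The other verum provers contribute 20 × 2 = 40 drug batches.
- At 28/12 the placebo count is 28 + 12 × 3 = 64, and the other verum provers contribute 27 × 2 = 54.

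The protocol gives no figure for chance matching, so there is none to reproduce.

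**Inputs assumed**
- p is the chance that one batch yields the exact same symptom with an inert drug, taken as 0.1% to 5%.
- q is the chance that one batch yields a similar symptom, taken as 2% to 20%.

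**Closed form, inert drug, 21/9**
- Unmatched by placebo: (1 − p)^48.
- Similar partner in another verum prover: 1 − (1 − q)^40.
- Mixed rule: the product of the two. A single definition uses p in both terms, or q in both.

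| p | q | Unmatched | Partner | Mixed rule | Exact for both | Similar for both |
|---|---|---|---|---|---|---|
| 0.1% | 10% | 0.953 | 0.985 | 94% | 4% | 0.6% |
| 0.2% | 5% | 0.908 | 0.871 | 79% | 7% | 7% |
| 0.5% | 5% | 0.786 | 0.871 | 69% | 14% | 7% |
| 1% | 5% | 0.617 | 0.871 | 54% | 20% | 7% |
| 1% | 10% | 0.617 | 0.985 | 61% | 20% | 0.6% |
| 1% | 2% | 0.617 | 0.554 | 34% | 20% | 21% |
| 2% | 5% | 0.379 | 0.871 | 33% | 21% | 7% |
| 5% | 5% | 0.085 | 0.871 | 7% | 7% | 7% |

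When p equals q the excess vanishes, as it should. At 28/12 (exponents 64 and 54), p of 0.5% to 1% with q of 5% to 10% gives 49% to 72%.

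**Simulation, inert drug, 21/9.** Assumptions: 20 to 35 body-system headings of unequal frequency, 20 to 50 equally likely exact variants in each, and a Poisson mean of 0.5 to 2 symptoms per batch. *Similar* means the same heading.
- About 71% to 98% of drug symptoms survive the exact placebo match.
- About 50% to 83% survive and also have a similar partner in another verum prover. With one definition on both sides the share is about 2% to 17%.
- With much finer groups (100 to 200 headings) the mixed rule gives about 20% to 60%.
- For Grade I (more than two provers, two sites, provers assumed evenly split), about 19% to 68% qualify if *similar* governs and 0% to 2% if *the same* governs.

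**The case against.** Feature H is one of nine descriptive features recorded for symptoms already accepted. It confirms nothing and does not control inclusion, since 14.1.1 keeps less frequent and less distinct symptoms in the data as well. This stands. A reader might infer that H is a confirmation rule, or that H and two-site Grade I are the plan's only evidence of recurrence. The protocol supports neither: 14.1.1 lists other recurrence criteria, and Grade I also admits symptoms seen in prior provings. The consequence that matters is the Grade I rank, and it depends on which half of an ambiguous bullet is followed.

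A reader might also take half to four-fifths as a property of this plan. It is not, because no symptom rate, heading count or variant count is in the protocol and the range moves widely with the assumptions.

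The chance of at least one recurrent symptom in an inert proving is also a poor argument. In the simulation it is 98% or more under the mixed rule. Under a single definition it can still be high: 18% to 100% with exact matching and 42% to 91% with similar matching.

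Blinded causality judgement (9.4.16) and the removal of unchanged symptoms (13.2) lower the background rate. They leave the mismatch of definitions in place.

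**Conclusion.** The concern holds as a mismatch between 13.4 on one side and 14.1.2 H and 14.1.3 on the other. Followed as written, the rules lean towards attributing background symptoms to the drug. The direction is firm wherever exact matches are rarer than similar ones.

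The size is conditional. It is about 50% to 83% against 2% to 17% under the main assumptions, and about 20% to 60% with finer headings. It is under 10% if exact matches are as common as 5% per batch. For Grade I it ranges from negligible to about two-thirds, and the choice between *similar* and *the same* decides which.

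This is not a matter left to a statistical analysis plan, because the protocol itself fixes both rules.

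**What to change.** 1. Write one matching definition and use it in 13.4, 14.1.2 H and 14.1.3. Decide whether Grade I means a similar symptom or the same one.
2. Assign each symptom its code before decoding, which is phase 3 in 13.3. Use that code both for the placebo comparison and for recurrence.
3. If a looser grouping is kept for H or Grade I, apply it equally to placebo-batch symptoms and show both counts.
4. In either case, report recurrence under drug beside recurrence under placebo, per batch. This is needed even with one definition. The repertory-subheading unit in 14.2 is nearly as fine as the exact rule, so adopting it alone would leave the placebo exclusion almost as weak.

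The cost is protocol wording and a little more coding and tabulation. No new data are needed. Fewer symptoms will qualify as recurrent.

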14.2 Quantitative analysis - Dose- biological response relationship

The principal analyses will employ the 'intention-to-treat' approach and will include all randomized participants in their randomly assigned groups. Comparison of the baseline characteristics among the two groups will use standard parametric & nonparametric statistical techniques.

The overall incidence of proving symptoms in each trial will be calculated by dividing the number of volunteers who had at least one reported proving symptom (pathogenetic effect) by the total number of volunteers taking the IPS (not on placebo)^[7].

The incidence of proving symptoms per volunteer is defined as the total number of findings claimed in the trial divided by the total number of subjects using the IPS (not placebo)^[7].

One proving symptom will be counted as a piece of information which could be included in a homeopathic repertory as an independent subheading. For instance, boring headache ameliorated by pressure is counted as one claim ^[7].

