8. STUDY DESIGN

The study will be prospective, parallel arm, randomized, placebo-controlled study.

Study Type:	Interventional
Allocation:	Randomized
Verum/placebo ratio(%):	Unbalanced (70/30)
Masking:	Double blind
Comparator:	Placebo
Endpoint Classification:	Disappearance of symptoms appearing during proving and subsequent symptom free period of 30 days.

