9.4.11 Potency for proving

In each proving study, the IPS will be proved in at least 2 potencies used in ascending order.

Pharmacopoeial drugs

The IPS can be proved in dilutions/potencies or tinctures, depending on the safety profile of the drug.

New drugs:

The IPS will be proved in potencies above the identified FSD.

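### Both quantitative outcome rates in Section 14.2 are defined on IPS takers only, with no placebo counterpart, so they cannot separate a drug effect from background symptoms

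*Protocol*

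**What the plan says.** Section 14.2 states that the principal analyses follow intention to treat and "will include all randomized participants in their randomly assigned groups". It then defines two outcome statistics:

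- The overall incidence takes the number of volunteers with at least one proving symptom and divides it "by the total number of volunteers taking the IPS (not on placebo".
- The incidence per volunteer takes all findings claimed in the trial, "divided by the total number of subjects using the IPS (not placebo".

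The section gives neither statistic for the placebo group. The one between-group comparison it names is this: "Comparison of the baseline characteristics among the two groups will use standard parametric & nonparametric statistical techniques".

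Placebo symptoms are used in two other places. Section 13.4 says that symptoms "generated in the drug group will be segregated from those of the control group", treats the verum arm's own placebo batch likewise, and rules that symptoms identical "in both drug and placebo will not be included as proving symptoms". Identity there means agreement in location, sensation, modalities and concomitants. Section 14.1.2 asks for separate listings under verum and placebo.

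The design table in Section 8 gives as endpoint: "Disappearance of symptoms appearing during proving and subsequent symptom free period of 30 days".

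**The concern.** The objective (Section 7) is to identify effects of the IPS, and the trial is titled randomised, double blind and placebo controlled. Section 9.4.7 justifies placebo control as protection against wrongly attributing symptoms to the IPS.

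A proving symptom is any change in mind or body for which causation by the IPS is possible (Section 13.2). Provers keep a daily record and are questioned daily during intake (Section 9.4.16). Some background reports are bound to be counted. A rate in IPS takers alone mixes these with any drug effect, and only the same rate on placebo can show how large the background is. If Section 14.2 is followed as written, a report can present a substantial incidence of proving symptoms for a substance that does nothing, with no figure beside it to reveal this.

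The endpoint in Section 8 does not fill the gap. It describes when observation and washout end, not whether the IPS produced symptoms.

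**Working it through.** **Inputs from the protocol.** Minimum 30 participants, 30% control, 20% dropout, 40 enrolled (Section 9.3); 70/30 allocation (Section 8); at least three batches (Section 9.4.13), of which one is placebo in the verum arm and all are placebo in the control arm (Section 9.4.9). With three batches a verum prover has two IPS batches and a control has three placebo batches. No background symptom rate, effect size, alpha or power is stated.

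**The protocol's own figure.** 30/(1 − 0.20) = 37.5, rounded up to 38. By arm, 21/0.8 and 9/0.8 round up to 27 + 12 = 39. The stated 40 agrees closely. The 70/30 split gives 21 v 9 of 30, or 28 v 12 of 40.

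**Inert IPS, no filter.** Assume a share p of batches gives at least one symptom, independently across batches. The incidence over two IPS batches is 1 − (1 − p)²:

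| p (assumed) | two IPS batches | three placebo batches, 1 − (1 − p)³ |
|---|---|---|
| 10% | 19% | 27% |
| 20% | 36% | 49% |
| 30% | 51% | 66% |
| 50% | 75% | 88% |
| 70% | 91% | 97% |

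If the same provers report in every batch, the two-batch figure falls to p itself.

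**Inert IPS, with the Section 13.4 filter.** Simulation with 21 verum and 9 placebo provers. Symptoms per batch are Poisson, drawn from K equally likely full descriptions. Any verum symptom that also appears in one of the 9 × 3 + 21 × 1 = 48 placebo batches is removed. The table shows the incidence left:

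| mean symptoms per batch | no filter | K = 50 | K = 200 | K = 1,000 |
|---|---|---|---|---|
| 0.2 | 33% | 28% | 32% | 32% |
| 0.5 | 63% | 46% | 59% | 63% |
| 1 | 86% | 53% | 79% | 85% |
| 2 | 98% | 43% | 91% | 98% |

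The filter lowers the rate substantially only when descriptions are few and coarse, and nowhere brings it near zero.

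**Exposure.** At p = 30% and no effect, two IPS batches against three placebo batches gives 51% v 66%, a spurious deficit on IPS of 15 points. Whole arms over three batches give 66% in both. The whole-arm contrast is diluted, however. If IPS batches ran at 50% and placebo batches at 30%, two matched batches would give 75% v 51%, a difference of 24 points. Whole arms would give 1 − 0.5² × 0.7 = 82.5% v 65.7%, about 17 points.

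**Precision.** Half-width = 1.96 × √[p(1 − p)(1/n₁ + 1/n₂)].

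- 28 v 12, whole arms: 31 points at p = 30%, 34 at p = 50%.
- 21 v 9, whole arms: 36 and 39 points.
- One potency at one batch position: if the placebo batch is equally likely at each of three positions, the higher of two potencies falls at batch 2 in 28/3, about 9, verum provers. Against 12 controls the half-width is 40 to 43 points.

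**The case against.** The strongest reply is that the main product of the trial is a qualitative symptom list. Section 14.1.1 says there is no measure of efficacy, and the Section 14.2 rates do not decide which symptoms enter the list. Descriptive one-arm rates can stand beside an intention-to-treat statement, and a test method may be left to an analysis plan. All of that is fair. What remains is that this protocol itself fixes the two definitions and fixes them without a control, and it names no between-arm outcome analysis to which the intention-to-treat sentence could apply.

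Some stronger readings are tempting but not supported:

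- *A reader might infer that the control arm is never used.* Sections 13.4 and 14.1.2 use it, as a filter and a listing.
- *A reader might infer that the first rate can exceed 100%, because its numerator is not expressly limited to IPS takers.* Proving symptoms are compiled after control-group symptoms have been segregated (Section 13.4, and the data analysis entry of the study summary), so placebo provers would not ordinarily be counted. The sentence only needs tightening.
- *A reader might infer that the incidence for an inert IPS would be high.* The level rests on an assumed background rate and on dependence between batches, and the Section 13.2 exclusions would lower it. Only a rate clearly above zero is supported.
- *A reader might infer that ascending potencies ("the IPS will be proved in at least 2 potencies used in ascending order") bias the dose comparison by a known amount.* Potency is tied to batch order, but nothing in the protocol gives a rate at which reporting changes over batches.

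**Conclusion.** The point holds in this form: placebo data never enter a quantitative outcome comparison, and both stated rates would be clearly positive for an inert substance. Under the assumptions shown, the overall incidence would be 19% to 91% over two independent batches without the filter, and about 28% to 98% with it. These figures are illustrations, since the protocol gives no background rate. That the rates cannot separate drug from background follows from the definitions alone.

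This must be fixed, because a stated rule yields a misleading result in a trial meant to attribute symptoms to the IPS. The tension with the intention-to-treat sentence is real but narrow: the denominators are as-treated, and no randomised outcome contrast is named.

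**What to change.** In Section 14.2:

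1. Compute both incidences on IPS and on placebo from the symptoms recorded blind at the sites, before the Section 13.4 subtraction. Limit each numerator to the same provers and batches as its denominator.
2. Match exposure. Count per batch, compare IPS batches with control-arm batches of the same batch number, and combine across batch numbers. Report the difference with a 95% confidence interval that allows for repeated batches per prover. Alternatively, compare whole randomised arms over all three batches as the intention-to-treat contrast, and state that the verum arm's placebo batch dilutes it.
3. Do not compare at least one symptom over two IPS batches with the same over three placebo batches.

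In Section 8, replace the endpoint entry with this exposure-matched incidence, IPS v placebo.

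The cost is protocol wording and one more table, since both arms' symptoms are already collected by batch. The drawback is a wide interval, and wider still for one potency at one batch position. That imprecision is a reason to show the interval rather than to omit the comparison. The qualitative compilation can stay as it is.
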